difference in the secondary endpoint of OS was also seen with a hazard ratio (HR) of 0.79 (95% CI: 0.62-1.00), $p = 0.051$. Median OS of subjects treated with talimogene laherparepvec was 4.4 months longer than those treated with GM-CSF (23.3 months for talimogene laherparepvec versus 18.9 months for GM-CSF) (Kaufman et al, 2014). Survival at 1, 2, 3, and 4 years in the talimogene laherparepvec arm was estimated to be 74%, 50%, 39% and 33%, respectively, and 69%, 40%, 30% and 21% in the GM-CSF arm, respectively. Median (range) time to response among the 78 subjects in the talimogene laherparepvec arm with a response was 4.1 (1.2 to 16.7) months, whereas among the 8 in the GM-CSF arm with a response, it was 3.7 (1.9 to 9.1) months. Fifty-four percent of talimogene laherparepvec objective responders and 48% of talimogene laherparepvec durable responders exhibited “interval progression”, which is transient locoregional or distant progression including appearance of new lesions, before ultimately achieving response (Ross et al, 2014; Kaufman et al, 2013). Subjects with HSV-1 seronegative or seropositive status at baseline had similar ORR (23.7 vs 28.6%), DRR (13.4 vs 17.7%, respectively), and OS HR ratio (0.79 vs 0.81) with talimogene laherparepvec (Kaufman et al, 2014; Andtbacka et al, 2013; data on file). The most common side effects in the OPTiM study were chills (talimogene laherparepvec, 49%; GM-CSF, 9%), pyrexia (43%; 9%), injection-site pain (28%; 6%), nausea (36%; 20%), influenza-like illness (30%; 15%), and fatigue (50%; 36%) (all treatment-emergent). Grade ≥ 3 adverse events occurred in 36% of subjects receiving talimogene laherparepvec and 21% of subjects receiving GM-CSF. The only grade 3/4 adverse events occurring in ≥ 5 subjects was cellulitis (talimogene laherparepvec, $n = 6$ [2.1%]; GM-CSF, $n = 1$ [$< 1\%$]). Of 10 fatal adverse events in the talimogene laherparepvec arm, 8 were attributable to disease progression. The remaining 2 fatal adverse events (sepsis in the setting of salmonella infection; myocardial infarction) were not considered treatment-related per investigator (Andtbacka et al, 2013). Subjects with HSV-1 seronegative or seropositive status at baseline had similar incidence of grade 3 and 4 (20.4 vs 17.7%) and serious adverse events (25.5 vs 28.0%) on talimogene laherparepvec (Andtbacka et al, 2013; data on file).

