no reported DLT during the DLT evaluation period (6 weeks following the first administration of ipilimumab). The most common adverse events were chills, fatigue, and pyrexia occurring in 11 subjects (58%) each. Grade 3 or 4 adverse events of any kind occurred in 6 subjects (32%). The only grade 3 or 4 adverse event occurring in more than one subject was grade 3 nausea in two subjects. Two subjects (11%) experienced possible immune-related grade 3 or 4 adverse events attributed either ipilimumab or the combination of ipilimumab and talimogene laherparepvec. There were no unexpected adverse events attributable to the combination therapy that have not been seen previously with either ipilimumab or talimogene laherparepvec individually. Of the subjects who experienced possible immune-related grade 3 or 4 adverse event, 1 subject experienced grade 3 hypophysitis attributed to ipilimumab and grade 3 adrenal insufficiency and grade 3 diarrhea, both of which were attributed to the combination of products. The other subject experienced grade 4 amylase and lipase elevations which were attributed to ipilimumab. These grade 3/4 adverse event rates and possible immune-related adverse event are consistent with what has been reported with ipilimumab alone (Hodi et al, 2010). One grade 5 adverse event of metastases to the central nervous system occurred during the treatment and safety follow-up period. Analysis performed at a median tumor follow-up time of 15.6 months revealed 9 objective responses (50%) with 4 confirmed CRs (33%) and DRR 44% by irRC (Puzanov et al, 2015). Median PFS was not yet reached with 50% of patients still without progression at 18 months. Median OS was not yet reached with 67% of patients still alive at 18 months. Median time to response was 4.1 months, and median duration of treatment was 13.3 weeks. Phase 2 of the study is currently ongoing. Primary analysis of the phase 2 portion of the study was recently reported (Chesney et al, 2017). 198 patients were randomized: 98 in the talimogene laherparepvec + ipilimumab arm and 100 in the ipilimumab arm. Baseline characteristics were generally balanced between the 2 arms. Thirty eight patients (39%) in the combination arm and 18 patients (18%) in the ipilimumab arm had an objective response (odds ratio, 2.9; 95% CI: 1.5 to 5.5; p = 0.002). Responses were not limited to injected lesions. Visceral lesion decreases were observed in 51 patients (52%) in the combination arm and 23 patients (23%) in the ipilimumab arm. Of 183 patients in the safety set (93 in the combination arm and 90 in the ipilimumab arm), the incidences of grade 3/4 treatment related adverse events were 45% in the combination arm and 35% in the ipilimumab arm. The most frequently occurring adverse events included fatigue (combination: 59%, ipilimumab: 42% respectively), chills (53%, 3%), diarrhea (42%, 35%), pruritus (40%,

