
^u Radiographic imaging (CT, PET/CT, or MRI) of the chest, abdomen, and pelvis, and CT or MRI of the brain are required at screening. Tumor assessments must also include all other sites of disease. The screening scans must be done within 28 days prior to enrollment. During treatment, radiographic imaging (CT or MRI) of the abdomen, pelvis, and chest, along with tumor assessments of all other sites of disease, (and CT or MRI of the brain if a subject has symptoms or signs suggestive of CNS metastases), will be performed independent of treatment cycle at week 12 (+1 week), and then every 12 weeks (+1 week) or more frequently if clinically indicated until confirmed iPD per modified irRC-RECIST ([Appendix F](#)) or start of new anticancer treatment. Imaging should not be adjusted for cycle initiation delays and performed according to the calendar. The imaging modality selected (eg, CT or MRI) should remain constant for any individual subject. Response or progression should be confirmed by repeated radiographic imaging ≥ 4 weeks after the first indication of response or progression. Radiographic imaging is required at the safety follow up visit if the subject ended treatment prior to confirmed iPD and has not had radiographic tumor imaging performed within 4 weeks (+1 week) of the visit. For subjects who discontinued treatment for any reason other than confirmed iPD, every effort should be made to complete radiographic assessments every 12 weeks (+1 week) or more frequently if clinically indicated during the long-term follow-up until documentation of confirmed iPD per modified irRC-RECIST ([Appendix F](#)), start of new anticancer therapy, or end of study whichever occurs first. The radiographic images will be collected for review of tumor response by a blinded independent central review committee.

^v Response (iCR, or iPR) or iPD to be confirmed by second consecutive response assessment no less than 4 weeks from the date of the first documented response or PD.

Approved

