* , iPD, iPD, * * , iPDci, *	iPD, iPD iPD, iSD, iPD, iPD iPD, iUE, iPD iPDci	iPD	Criteria for iBOR= iCR, iPR, or iSD not met. A consecutive confirmatory iPD must be no less than 4 weeks (28 days) later unless the initial progression qualified for iPDci.; iPDci = the last available iPD with “Nonconfirmed Disease Progression with Clinical Instability” as the reason for ending radiographic follow-up.
* , iSD, * iPD	iSD iUE, iSD iPD iUE, iPD	iUE	Criteria for iBOR=iCR, iPR, iSD, or iPD not met. iSD must be < 84 days from date of randomization.

Best overall response (BOR) per modified RECIST 1.1 (Phase 3)

BORs will be derived based on modified RECIST 1.1 ([Eisenhauer et al. 2009](#)) utilizing response evaluations obtained from BICR. Per RECIST 1.1, a confirmation of CR or PR by a consecutive subsequent tumor assessment will not be required for the derivation of BOR. Overall visit response assessments occurring on or after the start of the first subsequent anticancer therapy, including complete or partial removal/reduction of any target lesion which contained melanoma on pathology evaluation or pathology results were unknown, will not be included. The timepoint responses after initial PD will not be used to derive BOR. A timepoint response report of Non-CR/Non-PD (NN), a valid timepoint response for a subject who has been identified by BICR to have only non-target disease per RECIST 1.1, will be reported as is for analysis purposes. For the derivation of BOR, the overall visit response will be considered UE if it is SD earlier than 84 days after the date of randomization. BOR is defined as the best overall visit response up to and including the first overall visit response of PD in the following order: CR, PR, SD, NN, PD or UE.

Complete response rate (iCRR) per modified irRC-RECIST (Phase 3)

Complete response rate (iCRR) per modified irRC-RECIST is defined as the incidence of an iBOR of iCR per modified irRC-RECIST in the respective analysis set.

Disease control rate (DCR) per modified irRC (Phase 1b)

Disease control rate (DCR) per modified irRC is defined as the incidence of a BOR of CR, PR or SD in the respective analysis set.

Disease control rate (iDCR) per modified irRC-RECIST (Phase 3)

Disease control rate (iDCR) per modified irRC-RECIST is defined as the incidence of an iBOR of iCR, iPR or iSD in the respective analysis set.

Disease control rate (DCR) per modified RECIST 1.1 (Phase 3)

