Measurable tumor burden is defined as the sum of the diameters (longest for non-nodal lesions, short axis for nodal lesions) for all target lesions and up to 10 (maximum 5 per organ) new measurable lesions. The measurable tumor burden will be censored at the start of the first subsequent anticancer therapy, or at the time of complete or partial removal/reduction of any target lesion which contained melanoma on pathology evaluation or pathology results were unknown, whichever occurs first.

Depth of Response (DpR)

DpR is defined based on the maximum post-baseline measurable tumor burden decrease from baseline measurable tumor burden where maximum post baseline-measurable tumor burden decrease is categorized as: G0 = no shrinkage or increase, G1 = $>0 \leq 25\%$, G2 = $>25-50\%$, G3 = $>50-75\%$, G4 = $>75- < 100\%$, and G5 = 100%.

End of Study

Primary Completion: The primary completion date is defined as the date when the last subject is assessed or receives an intervention for the purposes of final collection of data for the primary endpoint(s).. The primary completion date is the date when data for the primary endpoints are last collected for the purpose of conducting the primary analysis.

If the study concludes prior to the primary completion date originally planned in the protocol (ie, early termination of the study), then the primary completion will be the date when the last subject is assessed or receives an intervention for evaluation in the study (ie, last subject last visit).

End of Study: The end of study date is defined as the date when the last subject across all sites is assessed or receives an intervention for evaluation in the study (ie, last subject last visit), following any additional parts in the study (eg, long term follow-up), as applicable.

Evaluable tumor assessment

An overall visit response other than iUE or UE.

Event of Interest (EOI) and Events of Clinical Interest (ECI)

EOIs are defined in version-controlled search strategies maintained by Global Regulatory Affairs and Safety (GRAAS) at Amgen for talimogene laherparepvec and those for ECIs for pembrolizumab will be provided by Merck before the analysis.

Investigational product (IP)

Investigational product (IP) refers to talimogene laherparepvec/placebo (also known as “Amgen IP”) and Pembrolizumab (also known as “non-Amgen IP”) in this study. IP is also referred as study drug, or study therapy.

Last date known to be alive

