For subjects not known to have died, their last date known to be alive will be determined as the latest date associated with clinic visits including, for example, but not limited to the following:

1. Survival status: Last subject status date if status of subject is “Alive”
2. End of study date if the primary reason for ending study is not “Lost to follow-up” or “Death”
3. Any Subsequent anti-tumor therapy initialization date
4. AE start or end date
5. Procedure and concomitant medication start/end date
6. Date of tumor assessments
7. Date of herpetic lesion swabbing
8. Visit date of vital signs; physical exam; ECOG; local lab and central lab
9. Date of last investigational product administration

Objective response rate (ORR) per modified irRC (Phase 1b)

ORR is defined as the incidence of a BOR of CR or PR per modified irRC in the respective analysis set. Subjects who do not have any post-baseline tumor assessments will be regarded as non-responders.

Objective response rate (iORR) per modified irRC-RECIST (Phase 3)

iORR is defined as the incidence of an iBOR of iCR or iPR per modified irRC-RECIST in the respective analysis set. Subjects who do not have any post baseline tumor assessments will be regarded as non-responders.

Objective response rate (ORR) per modified RECIST 1.1 (Phase 3)

ORR is defined as the incidence of a BOR of CR or PR per modified RECIST 1.1 in the respective analysis set. Subjects who do not have any post-baseline tumor assessments will be regarded as non-responders.

Overall Survival (OS)

Overall survival is defined as the interval from randomization (phase 3) or first dose (phase 1b) to death from any cause. Subjects without an event will be censored at the last known to be alive date.

Progression-free survival (PFS) per modified irRC (Phase 1b)

PFS per modified irRC is defined as the interval from first dose (phase 1b) to the earlier event of PD or death from any cause. Subjects without an event will be censored at their

last evaluable tumor assessment **if available; otherwise will be censored on Study Day 1.**

Progression-free survival (iPFS) per modified irRC-RECIST (Phase 3)

iPFS per modified irRC-RECIST is defined as the interval from randomization (phase 3) to the earlier event of iPD or death from any cause. Subjects without an event will be censored at their last evaluable tumor assessment **if available; otherwise will be censored on randomization date.**

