10.5.5 Additional Summaries

CR per BICR, and separately DpR per BICR, will be summarized for the Full Analysis Set. The proportion of subjects in each response level (CR analysis response levels: CR vs non-CR; DpR analysis response levels: G4/G5 vs G0/G1/G2/G3) will be provided by treatment arm. The between-treatment arm differences in proportions will be calculated and 95% CIs will be estimated using Wilson's score method for continuity correction.

Additionally, OS will be summarized by CR response level (CR vs non-CR) per BICR and treatment arm as well as by DpR response level (G4/G5 vs G0/G1/G2/G3) per BICR and treatment arm for the Full Analysis Set. The OS KM median estimates with the associated 95% CIs will be summarized for each level of the response within treatment arm.

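### SAP 10.5.5 reports median OS from randomization by response reached later, with no landmark or caveat, so guarantee time alone widens the responder gap in this descriptive table

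*SAP*

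**What the plan says.** SAP Section 10.5.5 (Additional Summaries) states that in the Full Analysis Set "OS will be summarized by CR response level (CR vs non-CR) per BICR and treatment arm", and likewise by depth of response, G4/G5 against G0 to G3. The statistic is given next: "The OS KM median estimates with the associated 95% CIs will be summarized for each level of the response within treatment arm". No test or hazard ratio between levels is planned.

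The definitions in SAP Section 6 set the clock and the groups:

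- Clock: "Overall survival is defined as the interval from randomization (phase 3) or first dose (phase 1b) to death from any cause".
- CR under modified RECIST 1.1: "BOR is defined as the best overall visit response up to and including the first overall visit response of PD in the following order". No confirmation is needed. Under modified irRC-RECIST, iCR needs a confirming assessment at least 28 days later. Section 10.5.5 does not say which of the two it uses.
- Depth of response: "DpR is defined based on the maximum post-baseline measurable tumor burden decrease from baseline measurable tumor burden".

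Protocol Table 6, footnote u, has on-treatment imaging "performed independent of treatment cycle at week 12 (+1 week), and then every 12 weeks (+1 week) or more frequently if clinically indicated". Protocol Section 10.5.3 counts subjects with no follow-up assessment as not having a complete response (for iCRR). The SAP does not say where subjects with no post-baseline measurement go in the depth-of-response split.

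Nothing visible in either document adds a landmark, a time-dependent handling of response or a caveat to this table. The OS sensitivity analyses in SAP Section 10.5.4.2 deal with informative censoring, subsequent therapy and unblinding. They concern the treatment comparison.

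**The concern.** Survival is timed from randomization, while membership of the better group is decided weeks or months later. A complete responder has, by construction, survived to the scan that showed the response, and that stretch counts as survival time for the responder group. A subject who dies first cannot become a complete responder and falls among the rest. This is guarantee-time (immortal-time) bias. It acts in one direction and needs no true link between response and survival.

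What is at stake is how the table is read. Medians with CIs set side by side by response level invite the conclusion that CR or deep response predicts longer life. Part of the gap would be an artefact, and the printed CIs do not reflect it.

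**Working it through.** **Inputs.** Median OS 28 months (control) and 40.4 (combination), OS hazard ratio 0.70, control survival 0.31 at month 48 and 0.27 at month 60: Protocol Section 10.2.2. CR rates 6% and 20%: same section, where they are iCRR planning assumptions, used here as a stand-in. Time to CR is not in the documents. The nearest figures are for any response on other regimens: "Median (range) time to response among the 78 subjects in the talimogene laherparepvec arm with a response was 4.1 (1.2 to 16.7) months" for the single agent, and for the ipilimumab combination "Median time to response was 4.1 months, and median duration of treatment was 13.3 weeks". They do not give time to CR and set no latest date for it.

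**The plan's own figure.** The control hazard from month 28 to 48 is ln(0.50/0.31)/20 = 0.0239 per month. In the combination arm the cumulative hazard at month 28 is 0.70 × 0.693 = 0.485. The remaining 0.208 accrues at 0.70 × 0.0239 = 0.0167 per month and takes 12.4 months. The median is 28 + 12.4 = 40.4, as stated.

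**Model.** Exponential OS with λ = ln 2/median, response unrelated to the hazard, and CR share r. Let S be overall survival and S_CR survival of eventual complete responders. Then S_non(t) = [S(t) − r·S_CR(t)]/(1 − r).

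*All responses at time g.* S_CR(t) = exp(−λ(t − g)) for t > g, so the CR median is g + median. At week 12, g = 12 × 7/30.4375 = 2.76 months.

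- Control: CR median 2.76 + 28 = 30.8. Non-CR median 28 + ln[(1 − 0.06e^(λg))/0.94]/λ = 28 − 0.18 = 27.8. Gap 2.9.
- Combination: CR median 43.2. Non-CR median 40.4 − 0.71 = 39.7. Gap 3.5.

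*Responses spread evenly from a to b, counted only if alive.* For t ≥ b, S_CR(t) = S(t)·λ(b − a)/[S(a) − S(b)]. Control, week 12 to month 12: [0.934 − 0.743]/(0.02476 × 9.24) = 0.835, so S = 0.417 at the CR median, which is 35.3 months.

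| Timing of CR | Control: CR vs non-CR (gap) | Combination: CR vs non-CR (gap) |
|---|---|---|
| All at week 12 | 30.8 vs 27.8 (2.9) | 43.2 vs 39.7 (3.5) |
| Status needs survival to week 16 (confirmed iCR) | 31.7 vs 27.7 (3.9) | 44.1 vs 39.4 (4.6) |
| Even, week 12 to month 12 | 35.3 vs 27.5 (7.8) | 47.7 vs 38.4 (9.3) |
| Even, week 12 to month 24 | 40.9 vs 27.0 (13.9) | 53.5 vs 36.6 (16.8) |

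Gaps are taken before rounding.

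**Curve shape.** Simulation with the protocol's piecewise control curve (hazard × 0.70 for combination) gives 3.1 / 3.5 at week 12, 3.8 / 4.8 at week 16 and 8.0 / 9.6 for the spread to month 12. Unconfirmed responses spread over scheduled scans from week 12 to week 96 give 13.4 / 21.4. The direction is the same throughout.

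**Landmark.** In the simulations a landmark removes the gap. At week 36, medians from the landmark are 27.9 to 28.1 (CR) vs 28.0 in control and 40.4 to 40.5 vs 40.4 in combination, for CR timings up to month 12.

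**Sampling error.** At 330 per arm there are about 20 (0.06 × 330) and 66 (0.20 × 330) complete responders. In 4,000 simulated trials the SD of the observed gap was about 9.7 months in control and 8.1 in combination. SAP Table 5 lists 692 subjects; at 346 per arm the counts are about 21 and 69.

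**The case against.** The strongest reply is that this is an additional summary. It carries no test, hazard ratio or alpha, and the SAP nowhere states that response predicts survival. Formal comparisons are confined to the two primary and three key secondary endpoints. Harm requires a reader to draw an inference that the plan does not make, and a footnote in the study report might be enough. This stands as a limit on severity.

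The size also rests on unknown response timing, which stands too. Stopping the spread at month 12 would be arbitrary, so the figures cannot be presented as a range. The week-12 row also combines confirmed-response rates with unconfirmed timing; the week-16 row shows the effect of confirmation.

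Four stronger readings are tempting and not supported:

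- That the primary OS comparison is biased. It compares randomized arms and does not use response.
- That any observed gap is wholly artefact. CR may truly go with longer survival; this table cannot separate the two.
- That sampling error outweighs the bias, or the reverse. In control, 7.8 months is below the SD of 9.7 and 13.9 is above it, so no limit in SD units is claimed.
- That the CR figures carry over to depth of response. The mechanism is the same, but no G4/G5 rate is given and the placement of unmeasured subjects is not stated.

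**Conclusion.** The concern holds, as a minor point. As written, the table shows a responder/non-responder gap in median OS even when response is unrelated to survival, because groups formed after randomization are followed from randomization. The direction follows from the definitions. The size does not: the spurious gap runs from 2.9 / 3.5 months (control / combination) to 13.9 / 16.8 across the timings tried. These are illustrations under exponential OS, the protocol medians and the 6% and 20% CR rates, and neither end is a bound. The observed gap will also be noisy, with an SD of about 8 to 10 months.

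**What to change.** Keep the table and make two additions to SAP Section 10.5.5.

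1. A note that the medians by response level cannot be read as an effect of response on survival.
2. A pre-specified landmark version for each of the two groupings, at a scheduled scan such as week 36. Take subjects alive and in follow-up at that date, classify them by response up to then, and measure OS from the landmark. Naming the date now avoids choosing it after seeing the results.

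The cost is one sentence and two tables, with no new data and no change to alpha or to the randomized comparisons. The downsides, under the same assumptions:

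- Subjects who die before week 36 (8.28 months) leave the added analysis: 1 − exp(−ln 2 × 8.28/28) = 18.5% of control and, with 40.4 in place of 28, 13.2% of combination. That is about 61 and 44 of 330.
- Later responders count as non-responders. If CR is spread to month 12, about 42% (control) and 41% (combination) of eventual complete responders are missing from the week-36 CR group, because they respond later or have died.
- About 12 of the 20 control complete responders would then remain, so that median would be imprecise.
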